### 16.3 Stratification Factors

CONFIDENTIAL

This document is confidential. Do not disclose or use except as authorized.

Study subjects will be stratified based on final pathological data for statistical analysis and outcomes reporting.

#### **16.4 Analysis of Primary Endpoints**

The primary endpoints are DFS and LRC at 3 and 5 years. Kaplan-Meier curves will be estimated for the standard therapy and the experimental therapy groups. Ninety-percent one-sided confidence intervals will be calculated for DFS at 3 and 5 years in the surgical and surgical/adjuvant therapy groups.

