#### Reporting of Serious Adverse Events

All investigators NHLBI must report both expected (protocol defined) and unexpected serious adverse events. All serious adverse events must be reported directly to the clinical center's IRB within 10 working days of knowledge of the event, or as dictated by the specific IRB policy, whichever is sooner. All deaths and unexpected serious adverse events must be reported to the IRB within 24 hours of knowledge of the event, or as dictated by the specific IRB policy, whichever is sooner. The investigators will notify the study sponsor of any deaths and unexpected serious adverse events via e-mail within 24 hours of receipt of the event. These events will also be reported to the DSMB chair within 72 hours of notification. All serious adverse events will be reported to the DSMB at least semi-annually, at the discretion of the DSMB. In addition, the investigators are expected to comply with their institutional policies and reporting requirements.

After recruitment of half of the study subjects (100) a full dataset analysis will be performed by the investigators and the statistical support group to ensure that outcomes are comparable to current standards. This will include statistical analysis of adverse events, recurrence rates after surgical therapy, outcomes of adjuvant therapy arms, and disease specific survival. Deviation from the proposed recurrence rates or overall disease specific survival will result in halting the trial. The primary endpoints are DFS and LRC at 3 and 5 years. Kaplan-Meier curves will be estimated for the standard therapy and the experimental therapy groups. Ninety-percent one-sided confidence intervals will be calculated for DFS at 3 and 5 years in the surgical and surgical/adjuvant therapy groups. The secondary endpoint of overall survival will be analyzed using Kaplan-Meier curves and a log-rank test for the difference between the two therapy groups. Five year OAS, DFS and LRC will be calculated using a log-rank test will be used to test for differences between the two treatment groups. Toxicity is another secondary endpoint. We will compute for each arm the toxicity rate and provide the corresponding 90% confidence intervals based on the exact binomial distribution.

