#### Stopping Boundaries: Based on stopping if the probability that recurrence exceeds 50% is $\geq 0.80$

The following are greater-than-or-equal boundaries:

a pair (n, m) means to stop if the number of adverse events after treating m patients is greater than or equal to n.

n (# events)	m (# patients)	n (# events)	m (# patients)
7	10	35	62
8	12	36	64
9	14	37	66

CONFIDENTIAL

This document is confidential. Do not disclose or use except as authorized.

10	16	39	69
11	18	40	71
13	21	41	73
14	23	42	75
15	25	43	77
16	27	44	79
17	29	46	82
19	32	47	84
20	34	48	86
21	36	49	88
22	38	50	90
23	40	51	92
25	43	52	94
26	45	54	97
27	47	55	99
28	49	55	100
29	51		
30	53		
32	56		
33	58		
34	60		
35	62		

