### 16.2 Sample Size/Accrual Rate

Sample size justification:

The proposed sample size of 100 for Group 1 has been determined to ensure that an upper bound for recurrence may be estimated with adequate precision, defined as within 8-12% of the true recurrence rate. The upper bound is estimated by the posterior probability of recurrence given the observed data, assuming a non-informative beta(1,1) prior distribution. The table below provides the upper 95% bound (from the Bayesian credible interval) assuming the true rate of recurrence is .1,.2,.3,.4, or .5 and 100 patients are studied.

True recurrence	Upper 95% bound
.1	.184
.2	.301
.3	.413
.4	.516

CONFIDENTIAL

This document is confidential. Do not disclose or use except as authorized.

[figure not shown]

.5

.614

The various specific aims outlined in Aim 1 share a common objective: determining rates of important measures of treatment response (progression-free survival, overall survival, local regional control and ultimate disease control) for patients treated with surgery alone and compare them to those expected in patients with similar diagnostic criteria. We will assess this overall objective by using a Bayesian approach to estimate the posterior probability distributions for each respective sub-aim based on observed outcomes. This approach permits estimating probabilities with which a specified rate of interest exceeds a threshold value (e.g.; 50% local regional control, 85% overall survival, etc.)

Our approach begins with the premise that surgery alone offers no improvement in expected outcomes. This is an exact correspondence to a "null hypothesis". We incorporate this assumption through a prior distribution for each suspected rate; for example, for Group I patients we would assume that the rate of local regional control (LRC) at three years is 50%. After the studies are conducted, each respective rate is combined with the "null" prior distribution through Bayes' Theorem to yield the posterior distribution for the rate. The table below depicts simulated results for the posterior LRC ( $\theta$ ) using 100 patients based on two differing assumptions: that LRC at three years is 50% ( $p=0.5$  shown on the left) and 85% ( $p=0.85$  shown on the right).

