Our expected sample size of 100 for Group I patients ensures that the inter-quartile range for the estimated probability distributions will extend from approximately 10-12 percentage points. This range is wider for smaller sample sizes (e.g. 30 or 50) but still less than 20 percentage points.

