#### **16.5 Analysis of Secondary Endpoints**

The secondary endpoint of overall survival will be analyzed using Kaplan-Meier curves and a log-rank test for the difference between the two therapy groups. Five year OAS, DFS and LRC will be calculated using a log-rank test will be used to test for differences between the two treatment groups.

Toxicity is another secondary endpoint. We will compute for each arm the toxicity rate and provide the corresponding 90% confidence intervals based on the exact binomial distribution.

Reporting and Exclusions

Not Applicable.

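### The analysis sections compare a standard-therapy group that the trial does not enrol, and the benchmark hypotheses in 16.1 have no pre-set criterion for success

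*Combined protocol and SAP*

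**What the plan says.** **Design.** The Study Design paragraph of 1.0 calls the trial non-randomized. Everyone has surgery. Under 4.2 and 5.0, pathology then assigns Group I (no adjuvant therapy), II (radiotherapy), IIIA or IIIB (chemoradiotherapy at two dose levels). No section enrols patients on standard therapy.

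**Analysis.** Section 16.4 states: "Kaplan-Meier curves will be estimated for the standard therapy and the experimental therapy groups". Its next sentence uses other group names: "Ninety-percent one-sided confidence intervals will be calculated for DFS at 3 and 5 years in the surgical and surgical/adjuvant therapy groups". Section 16.5 plans, for overall survival (OAS), "a log-rank test for the difference between the two therapy groups", and a further log-rank test for five-year OAS, DFS and local-regional control (LRC). Section 14.2 repeats all of this after its half-recruitment review. Section 12.0 speaks of comparing an experimental with a control arm. Section 11.1.1 defines OAS for the whole trial and for two sets of randomized patients.

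**Hypotheses.** Section 16.1 sets fixed benchmarks. For Group I they are OAS and ultimate disease control (UDC) above 85% at 5 years and LRC above 50%. For Groups II and III they are OAS and PFS above 85% at 5 years and LRC above 85%.

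**Threshold method.** Section 16.2 sets out to determine rates "for patients treated with surgery alone and compare them to those expected in patients with similar diagnostic criteria", and says its Bayesian approach permits "estimating probabilities with which a specified rate of interest exceeds a threshold value (e.g.; 50% local regional control, 85% overall survival, etc".

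**The concern.** A reader following 16.4 and 16.5 literally cannot draw the first curve, because there are no standard-therapy patients. A reader who substitutes the groups that do exist gets a computable p-value with the wrong meaning. Group I is defined by clear margins, few nodes and no LVI, PNI or extracapsular spread, and Groups II/III by the opposite. A survival difference between them would be expected from case mix alone, yet under the current labels it could be reported as a difference between therapies.

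The hypotheses the trial does state are one-sample statements. The method that suits them, in 16.2, stops at a posterior probability and does not say how large that probability must be. The same data can then be reported as meeting or missing a main hypothesis.

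**Working it through.** **1. Which two groups?** Three readings are possible.
- Standard against experimental: there are no patients in the first group.
- Randomized arms (11.1.1, 12.0): there are none.
- Surgical against surgical/adjuvant, as in the second sentence of 16.4: this is Group I against Groups II/III, and it is computable.

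Only the third survives. In it, pathology determines treatment completely, so no stratum contains both treatments at the same pathological risk. Section 16.3 stratifies the analysis by final pathology, but pathology is what defines the groups, so it cannot separate the two effects. A difference between groups also says nothing about whether either rate exceeds 85% or 50%.

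**2. The plan's only posterior cut-off.** The stopping table in 14.2 is headed "Based on stopping if the probability that recurrence exceeds 50% is" at least 0.80. With a beta(1,1) prior, P(rate > 0.5 | x of n) = 1 − F(0.5), where F is the Beta(1+x, 1+n−x) distribution function.
- 7 of 10 gives 0.887 and 6 of 10 gives 0.726, so the first pair (7, 10) reproduces.
- 55 of 100 gives 0.840 and 54 of 100 gives 0.787, so the last pair (55, 100) reproduces.

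This is a rule for halting on high recurrence. It is not a rule for declaring OAS, UDC, PFS or LRC successful.

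**3. What a missing cut-off leaves open.** Inputs from 16.1 and 16.2: n = 100 for Group I, benchmark 85%, beta(1,1) prior. Assumed: complete follow-up, and cut-offs c of 0.80, 0.90 and 0.95. The number required is the smallest x with P(rate > 0.85 | x) ≥ c. The false-positive rate is P(X ≥ x) for Binomial(100, 0.85), and power is the same tail at 0.90.

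| c | required | posterior at that x | false-positive rate | power at true 90% |
|---|---|---|---|---|
| 0.80 | 89 of 100 | 0.846 | 16% | 70% |
| 0.90 | 90 of 100 | 0.907 | 10% | 58% |
| 0.95 | 92 of 100 | 0.975 | 3% | 32% |

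An observed 90 of 100 has posterior probability 0.907. It meets the hypothesis at 0.90 and misses it at 0.95. For Group I LRC above 50%, the same three cut-offs need 55, 57 or 59 of 100, with false-positive rates of 18%, 10% and 4%.

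**4. The interval 16.4 already plans.** The one-sided 90% bound could serve as the criterion. With complete follow-up and the complementary log-log form, the lower bound is S^exp(1.2816·se), where se = √[(1−S)/(nS)] / |ln S|. For S = 0.90 and n = 100, se = √(0.1/90)/0.1054 = 0.316, and the bound is 0.90^1.50 = 85.4%. The smallest counts that clear 85%, with power at a true 90%, are:
- n = 100: 90 (bound 85.4%; 89 gives 84.2%), power 58%.
- n = 50: 46 (bound 85.4%; 45 gives 82.9%), power 43%.
- n = 30: 29 (bound 88.5%; 28 gives 84.3%), power 18%.

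Groups II/III have no planned size. The values 50 and 30 come from a remark in 16.2 about precision ("This range is wider for smaller sample sizes (e.g. 30 or 50) but still less than 20 percentage points") and are illustrative. Section 14.2 ("After recruitment of half of the study subjects (100) a full dataset analysis will be performed") implies 200 in all, which would leave 200 − 100 = 100 outside Group I, but no section says so.

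**5. Size of the log-rank problem, illustration only.** The survival rates are assumed, as is a two-sided 5% level, which the plan does not state. If risk alone made 5-year survival 95% against 85%, simulation (exponential times, censoring at 5 years, 10,000 runs) rejects in 67% of trials with 100 against 100 patients and 55% with 100 against 50. At 92% against 85% it rejects in 35% and 28%.

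**The case against.** The best defence is that this is leftover two-arm wording. The second sentence of 16.4 names the right groups, and the objectives in 1.1 mostly ask to determine rates, for which estimation suffices in phase II. The sample size rests on precision, and a posterior probability can be reported without a pass mark. Much of this stands. Renaming the groups cures the labels, and estimation alone would be acceptable if 16.1 did not state hypotheses. But 16.1 does state them, with numbers, and renaming does not turn a risk-group log-rank test into a test of them.

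A reader might also infer more than the documents support:
- That the 16.1 hypotheses have no planned analysis. They do for surgery alone: 16.2 commits to a Bayesian assessment of those aims. What is missing is the probability that counts as success, and any statement that the method covers Groups II/III.
- That OAS cannot be analysed because nobody is randomized. The whole-trial population in 11.1.1 is usable; only the two randomized populations are empty.
- That LRC has no time point. Section 16.1 lists it at 3 years as primary and at 5 years as secondary; only the hypothesis clause is undated.
- That the log-rank test has a known chance of misleading. The rejection rates above depend on survival rates found nowhere in the documents.

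**Conclusion.** The point holds and should be fixed. Sections 16.4, 16.5, 14.2, 12.0 and 11.1.1 describe a comparator or a randomization the trial does not have. The one feasible between-group test confounds treatment with assigned risk and addresses no stated hypothesis. Leaving the success criterion open moves the Group I survival requirement from 89 to 92 of 100 and the false-positive rate from 16% to 3%, over assumed cut-offs of 0.80 to 0.95 with a beta(1,1) prior and complete follow-up.

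For Groups II/III the only within-group efficacy interval planned is the one for DFS. DFS is not defined in 11.1.1, and 16.4 attaches no benchmark to it. If DFS means PFS, the interval bears on the PFS hypothesis; OAS and LRC in those groups have no benchmark analysis.

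Which patients form the intent-to-treat population, and which prior 16.2 intends, are separate questions on which this conclusion does not depend.

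**What to change.** 1. In 16.4, 16.5, 14.2 and 12.0, replace the terms *standard therapy*, *experimental therapy* and *control arms* with Group I (surgery alone) and Groups II/III (surgery plus adjuvant therapy). Label any between-group curve or log-rank test a descriptive comparison of risk groups, not a treatment effect. In 11.1.1, change *randomized* to *assigned*.
2. Test the 16.1 hypotheses by one-sample comparison with their own benchmarks: Group I LRC above 50%, OAS and UDC above 85%; Groups II/III OAS, PFS and LRC above 85%. Keep each endpoint's primary or secondary status once 1.1, 16.1, 16.4 and 16.5 have been reconciled, since they now differ.
3. Fix one success criterion in advance. It can be a posterior cut-off for the 16.2 method, extended to Groups II/III, or the one-sided 90% Kaplan-Meier lower bound at the level 16.4 already uses, which also handles censoring.
4. Treat UDC as a proportion at a stated time, because 11.1.1 defines it as status at analysis. Date the LRC hypothesis, and say whether DFS means PFS.

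The cost is wording and one pre-specified rule. Between-group p-values can no longer be presented as treatment effects. Because Groups II/III have no planned size, the plan should say that their precision, and their power against 85%, may be low.

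### The precision figure that justifies n = 100 in section 16.2 fits neither the 95% bound it names nor the one-sided 90% interval that sections 16.4 and 14.2 will report

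*Combined protocol and SAP*

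**What the plan says.** Section 16.2 (Sample Size/Accrual Rate) sizes Group I for estimation: "The proposed sample size of 100 for Group 1 has been determined to ensure that an upper bound for recurrence may be estimated", with the target "adequate precision, defined as within 8-12% of the true recurrence rate". The method is a posterior bound "assuming a non-informative beta(1,1) prior distribution". The table is introduced by "The table below provides the upper 95% bound (from the Bayesian credible interval" and prints .184, .301, .413, .516 and .614 for true recurrence of .1, .2, .3, .4 and .5. The text does not say whether this bound is a one-sided 95% quantile or the upper end of a two-sided 95% interval.

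The same section extends the Bayesian approach to progression-free survival, overall survival, local regional control and ultimate disease control. There it describes a second, null-centred prior: "for Group I patients we would assume that the rate of local regional control (LRC) at three years is 50" per cent. It says that probabilities of exceeding a threshold can be estimated, but gives no probability cut-off.

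Section 16.4 (Analysis of Primary Endpoints) plans Kaplan-Meier curves and "Ninety-percent one-sided confidence intervals will be calculated for DFS at 3 and 5 years in the surgical and surgical/adjuvant therapy groups". Section 14.2, under Reporting of Serious Adverse Events, carries the same sentence: "Ninety-percent one-sided confidence intervals will be calculated for DFS at 3 and 5 years".

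Section 16.1 places the Group I benchmark of more than 85% on 5-year overall survival and ultimate disease control, and the benchmark of more than 50% on local regional control.

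**The concern.** A sample-size argument based on precision is useful only if it describes the interval that will be reported. Here the sizing uses a Bayesian 95% bound on recurrence and the analysis uses a frequentist one-sided 90% interval on DFS, an endpoint that section 11.1.1 does not define. A one-sided 90% limit is the end of a two-sided 80% interval, so it matches neither reading of a 95% bound.

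Two things are at stake. The reader is told that 100 patients give a precision that the reported interval will not have. And with two levels in the plan and no rule linking either to the benchmarks, the level used for interpretation could be chosen after the counts are known.

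**Working it through.** **Inputs.** From 16.2: n = 100, Beta(1,1) prior, true recurrence .1 to .5, the printed bounds, and the 8 to 12 point target. From 16.4 and 14.2: one-sided 90%. Assumptions: every patient is evaluable without censoring, and the observed number of recurrences is x = 100 × the true rate.

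**Step 1: reproduce the 16.2 table.** The posterior is Beta(1 + x, 101 − x), and the upper bound at level q is its q-quantile.

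| True rate | Printed | One-sided 90% | One-sided 95% | Upper end of two-sided 95% (97.5% quantile) |
|---|---|---|---|---|
| .1 | .184 | .148 | .162 | .175 |
| .2 | .301 | .258 | .275 | .289 |
| .3 | .413 | .363 | .381 | .396 |
| .4 | .516 | .464 | .483 | .498 |
| .5 | .614 | .563 | .581 | .596 |

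The printed column matches neither 95% reading. Its entries sit at the 98.6% to 99.0% posterior quantiles. Exact, Wilson and normal-approximation limits, and averaging over binomial sampling, do not reproduce all five values either. Nor does another n: at one-sided 95% the n that would give each printed value falls from about 61 (at .1) to 49 (at .5), and at the 97.5% quantile from about 82 to 71.

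**Step 2: distance from true rate to bound, in percentage points.**

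- Printed table: .184 − .1 = 8.4, then 10.1, 11.3, 11.6, 11.4. This is where 8 to 12 comes from.
- One-sided 90% (16.4 and 14.2): 4.8, 5.8, 6.3, 6.4, 6.3.
- One-sided 95%: 6.2, 7.5, 8.1, 8.3, 8.1.
- Upper end of two-sided 95%: 7.5, 8.9, 9.6, 9.8, 9.6.

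The 8 to 12 points agree with the printed table, but not with a 95% bound on either reading, and not with the 16.4 level.

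**Step 3: would the level matter for a benchmark?** This step is conditional, because the plan states no such rule. Suppose a lower bound on a Group I success rate had to exceed .85, with x successes in 100. The Beta(1,1) lower bounds are:

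| Successes | One-sided 90% | One-sided 95% | Lower end of two-sided 95% |
|---|---|---|---|
| 90 | .8516 | .8378 | .8254 |
| 91 | .8630 | .8497 | .8376 |
| 92 | .8745 | .8616 | .8499 |
| 93 | .8862 | .8738 | .8624 |

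So 90 and 91 clear .85 at one-sided 90% but not at one-sided 95%; 92 joins them if the 95% interval is two-sided. Exact binomial limits give the same sets (90 of 100: .8501 and .8363; 91 of 100: .8616 and .8482).

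Other methods do not. Plain Greenwood without censoring at 90 of 100 has standard error √(.9 × .1/100) = .03 and gives .900 − 1.282 × .03 = .8616 and .900 − 1.645 × .03 = .8507. Both clear, while 89 fails at both levels, so no count is disputed at one-sided 95%. Comparing one-sided 90% with one-sided 95%, Wilson gives only 90, Greenwood on the log scale only 89, and log-log Greenwood 90 and 91.

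**The case against.** The strongest reply is that sizing for precision at one level and reporting a phase II interval at another is not in itself an error. The plan also uses 90% intervals for toxicity in 16.5, so 90% may be deliberate. That stands: preferring 95% to 90% is a matter of choice, and this point does not require it.

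The second reply is that the excess of 8 to 12 points over the correct values comes mainly from a faulty table, not from the 90/95 difference. That also stands. The table would need correcting even if 16.4 said 95%.

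A reader might go further and infer that 90 or 91 successes in 100 beat the 85% benchmark under one section and fail under the other, with a corresponding difference in false-positive risk. The documents do not support this:

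- Section 16.2 uses its bound only for precision, and 16.4 only says that intervals will be calculated. Neither makes clearing 85% or 50% a criterion.
- For Group I the 85% benchmark belongs to 5-year overall survival and ultimate disease control, while the 90% interval is for DFS. Section 16.5 gives overall survival Kaplan-Meier curves and a log-rank test, with no interval level.
- The benchmark for PFS and LRC of more than 85% applies to Groups 2 and 3, for which no sample size is given.
- The disputed counts depend on the interval method, which 16.4 does not name.

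**Conclusion.** The point holds in a limited form. The plan uses two unreconciled specifications for its rates, and the precision that justifies n = 100 describes neither of them. The printed bounds exceed a one-sided 95% bound by 2.2 to 3.3 points, the upper end of a two-sided 95% interval by 0.9 to 1.8 points, and the one-sided 90% bound of 16.4 by 3.6 to 5.2 points (for example .184 − .148 and .516 − .464). These figures rest on n = 100, the stated Beta(1,1) prior and complete follow-up; censoring would widen the reported interval.

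The error runs in the safe direction. Correctly computed, 100 patients give tighter bounds than claimed, so the sample size does not have to rise. The effect on conclusions is only conditional: if a bound-exceeds-85% rule were adopted with Beta(1,1) or exact limits, 90 to 91 of 100 (90 to 92 if the 95% interval is two-sided) would be classified differently at the two levels. Other methods give a smaller or empty set.

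**What to change.** Before any outcome analysis, declare one level, one sidedness and one interval method for the primary rates. State which endpoints it applies to, and use it in 16.2, 16.4 and the copy in 14.2. Then replace the 16.2 column and the 8 to 12 figure to match:

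- If one-sided 90% is kept: .148, .258, .363, .464, .563, with precision of about 5 to 6.5 points.
- If one-sided 95% is chosen: .162, .275, .381, .483, .581, about 6 to 8 points.
- If two-sided 95% is meant: .175, .289, .396, .498, .596, about 7.5 to 10 points.

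These columns are for Beta(1,1); recompute them if another method is declared. Any of these choices is acceptable provided that it is fixed in advance.

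The cost is changed wording and one restated table, with no extra patients. Keeping 90% costs nothing more. Choosing one-sided 95% makes the reported bound wider, by 1.4 to 1.8 points over recurrence of 10% to 50% (for example .162 − .148 = .014 and .381 − .363 = .018).
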